**STUDY SPONSOR**

**ZIMMER GMBH  
[name]  
[name]  
SWITZERLAND**

Complete Protocol Title	Randomized controlled study comparing the Taperloc Complete versus the Taperloc Complete Microplasty
Protocol Number	ORTHO.CR.GH60
Short Protocol Title	Randomized controlled study comparing the Taperloc Complete versus the Taperloc Complete Microplasty
Sponsor	Zimmer GmbH, [name]
Manufacturer	Biomet Orthopedics, [name]
Study Device(s)	Taperloc Complete Microplasty PPS-Bonemaster Taperloc Complete Reduced Distal PPS- Bonemaster
Technical Documentation Reference Number	Reference can be found on Post-market surveillance Plan (PMSP)
Study Objectives/Endpoints	
Primary endpoint: Migration of the prosthesis over two years based on RSA data.
 
Secondary endpoints:
 
 
The prevalence of malalignment, incorrect sizing, subsidence and intraoperative fractures at the direct postoperative visit.
 
Survival of the hip prosthesis within 2 years.
 
Clinician based outcomes (HHS and radiological evaluation) and patient based outcomes (HOOS, EQ5D, Oxford Hip score, Forgotten Joint score) at each visit.
 

Indications/Target Population	Subjects with osteoarthritis of the hip scheduled for a primary total hip arthroplasty (THA) who are willing to participate in the study. Subjects have to meet all the in- and exclusion criteria of the study.
Inclusion/Exclusion Criteria	
Inclusion criteria
 
In order to be eligible to participate in this study, a subject must meet all of the following criteria. These are standard indications for usage of the Taperloc Complete and Taperloc Microplasty stem.
 
Subjects with one of the following indications:
 
 
Non-inflammatory degenerative joint disease including osteoarthritis, avascular necrosis and rheumatoid arthritis.
 
Correction of functional deformity.
 
 
Additional inclusion criteria include:
 
 
Male or female
 
≥ 18 and ≤ 70 years of age
 
Subjects willing to return for follow-up evaluations.
 
Subjects able to read and understand Dutch language.
 
 
Exclusion criteria
 
A potential subject who meets any of the following criteria will be excluded from participation in this study.

	
 
• active Infection (or within 6 weeks after infection)
 
• Sepsis
 
• Osteomyelitis
 
• Uncooperative patient or patient with neurologic disorders who are incapable of following directions
 
• diagnosed Osteoporosis or Osteomalacia
 
• Metabolic disorders which may impair bone formation
 
• Distant foci of infections which may spread to the implant site
 
• Rapid joint destruction, marked bone loss or bone resorption apparent on roentgenogram
 
• Vascular insufficiency, muscular atrophy or neuromuscular disease.
 

Study Design	
A single-centre, randomized controlled post market surveillance study:
 
 
• Group 1: Taperloc Complete PPS-Bonemaster, Reduced Distal, Type 1 Taper (n=25)
 
• Group 2: Taperloc Complete Microplasty Reduced Distal, PPS-Bonemaster, Type 1 Taper (n=25)
 
 
In both groups, the G7 acetabular cup is used with Polyethylene E1 articulation.

Clinical Phase	Post-market
Sample Size	50 subjects in total, 25 study subjects implanted with the study device per cohort.
Length of Study	3 years (1 year of enrolment and 2 years of follow-up)
Materials and Methods	All included patients will be assessed preoperatively and directly postoperative. Follow-up will take place at 6-weeks, 1 and 2 years postoperatively.
Data Collection	Electronic
Statistical Reporting	Data collected will be summarized and reported to the participating investigator. Zimmer Biomet or its designee will conduct statistical analysis. Survivorship will be evaluated using Kaplan-Meier. Implant migration will be evaluated using Roentgen Stereogrammetric Analysis (RSA).
Scores/Performance Assessments	HHS, HOOS, EQ5D, Oxford Hip score, Forgotten Joint Score.
Standards	
The PMCF is compliant with the below:
 
 
• ISO 14155: 2020 - Clinical investigation of medical devices for human subjects - Good clinical practice.
 
• The Declaration of Helsinki (DoH) - Ethical principles for medical research involving human subjects.
 

Study Funding	Zimmer Biomet makes funding for this clinical study available to support clinical data collection, IRB/EC review fees and other expenses associated with the conduct and execution of this study protocol as outlined in the fully executed Clinical Trial Agreement.

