## **STATISTICAL METHOD**

Data will be analyzed using the “Statistical Package for the Sciences” version 20.0 or higher. Differences will be 2-tailed tested and alpha is set on 0.05. Data will be presented as per protocol (intention-to-treat) and as treated analysis (treatment eventually received).

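### Subsidence prevalence is timed to the first scheduled assessment with the stem in place, with no earlier reference image stated, so this component cannot compare the two stems

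*Combined protocol and SAP*

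**What the plan says.** The synopsis row Study Objectives/Endpoints gives secondary endpoint 1 as: "The prevalence of malalignment, incorrect sizing, subsidence and intraoperative fractures at the direct postoperative visit". One time point governs all four items.

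The synopsis row Materials and Methods sets the schedule: "All included patients will be assessed preoperatively and directly postoperative. Follow-up will take place at 6-weeks, 1 and 2 years postoperatively".

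Two other endpoints bear on stem movement. The primary is stated as: "Primary endpoint: Migration of the prosthesis over two years based on RSA data". Secondary endpoint 3 is stated as: "Clinician based outcomes (HHS and radiological evaluation) and patient based outcomes (HOOS, EQ5D, Oxford Hip score, Forgotten Joint score) at each visit". It includes radiological evaluation but does not name subsidence.

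The Statistical Method section adds nothing specific to subsidence. Its general rule is: "Differences will be 2-tailed tested and alpha is set on 0.05". Under Descriptive analysis, every outcome is to be given with a 95% confidence interval. The text gives no reference image, definition, cut-off or measurement method for subsidence, and no imaging schedule.

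**The concern.** Malalignment, incorrect sizing and intraoperative fracture can be judged at a single examination. Subsidence cannot: it is movement of the stem between two examinations. The plan asks for its prevalence at what appears to be the first of them, so there is nothing to measure the movement from.

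Two things are at stake. The trial loses radiographic subsidence as a supportive result beside the RSA data, whichever stem sinks more later. And because every outcome is to carry a confidence interval, the report could show no subsidence in either arm with an interval attached. A reader could take that as evidence of stability when it follows from the timing alone.

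**Working it through.** **Step 1. Order the assessments (synopsis, Materials and Methods).**

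| Assessment | Stem in place? | Earlier scheduled assessment with stem in place |
|---|---|---|
| Preoperative | No | – |
| Direct postoperative | Yes | 0 |
| 6 weeks | Yes | 1 |
| 1 year | Yes | 2 |
| 2 years | Yes | 3 |

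Four assessments have the stem in place. Secondary endpoint 1 uses the only one with no predecessor. The other three can each be compared with the direct postoperative image.

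**Step 2. Apply the definition.** Subsidence at visit *t* is position at *t* minus position at the reference.
- If the direct postoperative image is the reference, the difference at that visit is zero for every patient.
- If there is no reference, the difference is undefined.

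Neither case depends on which stem was implanted.

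**Step 3. What would be reported in the first case.** With 25 per arm (synopsis, Sample Size), the table is 0/25 versus 0/25. The two-sided Fisher p-value is 1.00. The upper limit of the two-sided exact 95% interval is 1 − 0.025^(1/25) = 0.137, or 13.7% in each arm. That limit reflects only the sample size.

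**Step 4. What a re-timed endpoint could support.** This does not measure the timing flaw; it bears on how the corrected endpoint should be labelled. With 0 events in one arm and *b* in the other, the two-sided Fisher p-value is 2 × C(25,b)/C(50,b).
- *b* = 5: 2 × 53,130/2,118,760 = 0.0502, just short of significance at 0.05.
- *b* = 6: 2 × 177,100/15,890,700 = 0.0223.

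So against 0/25, the other arm needs 6/25 (24%). With 1 event in one arm, 7 in the other gives p = 0.0488.

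Exact power is the sum of Bin(a; 25, p₁) × Bin(b; 25, p₂) over all pairs (a, b) for which Fisher p ≤ 0.05. The documents give no subsidence rates, so these are assumptions shown as a range:

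| Assumed true rates | Power |
|---|---|
| 5% vs 15% | 0.07 |
| 5% vs 20% | 0.20 |
| 5% vs 30% | 0.55 |
| 5% vs 40% | 0.82 |

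Only a very large difference would be detected reliably, so the re-timed endpoint is suited to description.

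The plan offers no figure of its own to reproduce here: the sample size of 50 is stated without an effect size, power or event rate.

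**The case against.** The strongest reply is that the plan may be incomplete rather than wrong. No day or window is given for the direct postoperative visit, and no imaging schedule is given. If an intraoperative image exists, or an earlier film precedes a visit held some days after surgery, some comparison would be possible. This stands as a limit: the first-image status is inferred. But no such image is stated, and the endpoint as written cannot be computed usefully without one.

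Second, RSA already measures migration over two years, and radiological evaluation is listed at each visit. Both are true and both reduce the loss. They do not repair the endpoint: subsidence is named only in secondary endpoint 1, at the one visit where it has no stated reference.

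Third, the power figures describe a re-timed endpoint at assumed rates, for a test that is not being recommended. That is correct. They justify the descriptive label and nothing more.

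Fourth, simply deleting subsidence from the list would also remove the inconsistency. It would, but it gives up the supportive radiographic result that the sponsor evidently wanted.

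**Conclusion.** The concern holds. As written, the subsidence component of secondary endpoint 1 is zero or undefined in both arms and carries no information about the difference between the stems. This is a timing rule that does not work, not only a missing detail.

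The size is modest: 1 of 4 components of 1 of 3 secondary endpoints. The primary endpoint, the sample size and the other three components are untouched. It should be corrected, but it does not threaten the trial's main conclusion.

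The conclusion rests on two assumptions: that subsidence means a change between two examinations, and that no image with the stem in place precedes the direct postoperative one. The second is inferred from the visit schedule, so confidence is moderate.

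**What to change.** - Take subsidence out of the direct postoperative list. Keep malalignment, incorrect sizing and intraoperative fracture there.
- Report the prevalence of radiographic subsidence at 6 weeks, 1 year and 2 years relative to the direct postoperative image. Fix the measurement definition and cut-off before analysis.
- Give it per arm with 95% confidence intervals, labelled descriptive and supportive of the RSA primary endpoint, with no hypothesis test at the three visits.
- If an earlier reference image does exist, name that image and the cut-off instead.

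The cost is low but goes beyond wording. A radiographic definition and cut-off must be chosen, and the result will overlap with the primary endpoint. No extra visit is needed, provided the radiological evaluation already listed at each visit yields usable images; the sponsor should confirm this, since no imaging schedule is given. Keeping it descriptive avoids adding three tests under the single stated alpha of 0.05.

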## **STATISTICAL METHOD**

Data will be analyzed using the “Statistical Package for the Sciences” version 20.0 or higher. Differences will be 2-tailed tested and alpha is set on 0.05. Data will be presented as per protocol (intention-to-treat) and as treated analysis (treatment eventually received).

### **Descriptive analysis**

Descriptive analysis will be performed to report baseline characteristics and outcome measures. Continuous data (e.g. age, BMI,): mean  $\pm$  SD or medians and IQR (depending on normality). Categorical data (e.g. gender, ASA): number and frequencies will be reported for treatment groups.

The quantitative variables obtained from the clinical evaluation (HHS, HOOS, EQ-5D, Oxford Hip Score and Forgotten Joint Score) will be tabulated and analysed as mean, standard deviation, minimum and maximum values. Complications and other clinical relevant information will be documented as known variables. All outcomes will be reported with 95% confidence intervals.

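### No baseline-adjusted between-arm comparison is planned for the five hip and quality-of-life scores; ANCOVA would cost about 1% in interval width at worst and could narrow it appreciably

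*Combined protocol and SAP*

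**What the plan says.** The synopsis row Study Objectives/Endpoints lists as the third secondary endpoint: "Clinician based outcomes (HHS and radiological evaluation) and patient based outcomes (HOOS, EQ5D, Oxford Hip score, Forgotten Joint score) at each visit". The Materials and Methods row gives the visits: "All included patients will be assessed preoperatively and directly postoperative", and then "Follow-up will take place at 6-weeks, 1 and 2 years postoperatively". Neither row lists which instrument is taken at which visit. Read together, they imply that the scores are taken before surgery as well as after it.

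On analysis, the Statistical Method section sets a general rule: "Differences will be 2-tailed tested and alpha is set on 0.05". The Descriptive analysis section opens with "Descriptive analysis will be performed to report baseline characteristics and outcome measures". It then says that the five scores "will be tabulated and analysed as mean, standard deviation, minimum and maximum values", and closes with "All outcomes will be reported with 95% confidence intervals". It does not say whether those intervals are for each arm or for the difference between arms.

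The section on Primary and Secondary Endpoint Analysis defines which cases are analysed and gives no method. Where the plan does name methods, they are for other outcomes: Kaplan-Meier under Survivorship, and chi-square and Fisher's exact under Study Safety for adverse events.

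**The concern.** This is a randomised comparison of two stems, so readers will want the difference between arms on the scores. The plan implies such a comparison through its two-tailed rule, but it fixes neither the model nor the effect measure. An analyst could compare follow-up scores, compare changes from baseline or fit ANCOVA, and could choose among these after seeing the data.

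Precision is also at stake. With only 25 subjects per arm, intervals for the scores will be wide. A preoperative value of the same score is the obvious covariate, and it is apparently collected already. If it predicts the follow-up score even moderately, leaving it out gives up precision that needs no further patients.

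**Working it through.** **Inputs from the documents.** 25 subjects per arm, 50 in total (synopsis, Sample Size); two-sided alpha 0.05 (Statistical Method); 95% intervals (Descriptive analysis). The documents give no precision or power figure for the scores, so there is no figure of the plan's own to reproduce.

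**Assumptions.** The correlation r between preoperative and follow-up score is not given; 0, 0.3, 0.5 and 0.7 are tried. No SD is given, so results are in units of the follow-up SD. The SD is taken as equal at both times, which matters only for the change score. Follow-up is taken as complete, except in the sensitivity case below.

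**Formulas for the 95% CI half-width of the between-arm difference**, n = 25, N = 50:

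- Follow-up score only: t(48) × √(2/n) = 2.0106 × √0.08 = 2.0106 × 0.2828 = 0.569 SD, whatever r is.
- Change score: t(48) × √[(2/n) × 2(1 − r)] = 0.569 × √[2(1 − r)].
- ANCOVA: t(47) × √[(2/n)(1 − r²)(1 + 1/(N − 4))] = 2.0117 × 0.2828 × √(1 + 1/46) × √(1 − r²) = 0.575 × √(1 − r²). The factor 1 + 1/46 allows for chance imbalance in the covariate, and 47 df for the extra parameter.

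| Assumed r | Follow-up only | Change score | ANCOVA | ANCOVA vs follow-up only | Equivalent n per arm, follow-up only |
|---|---|---|---|---|---|
| 0 | 0.569 | 0.804 | 0.575 | +1% | about 24 |
| 0.3 | 0.569 | 0.673 | 0.549 | −3.5% | about 27 |
| 0.5 | 0.569 | 0.569 | 0.498 | −12% | about 33 |
| 0.7 | 0.569 | 0.441 | 0.411 | −28% | about 48 |

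The last column is 25 × (follow-up-only width / ANCOVA width)²; for r = 0.5, 25 × (0.569/0.498)² is about 33.

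**Break-even against follow-up only.** Setting the two widths equal gives (2.0117/2.0106)² × (1 + 1/46) × (1 − r²) = 1, so r is about 0.15. Below that, ANCOVA is slightly wider.

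**Against the change score.** ANCOVA is narrower by 28%, 19%, 12% and 7% at the four correlations.

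**Check by simulation.** With normally distributed scores and 10,000 trials per correlation, the ratio of ANCOVA to follow-up-only width was 1.011, 0.964, 0.875 and 0.722. The formulas give 1.011, 0.965, 0.876 and 0.722.

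**Sensitivity.** If only 20 per arm have complete data (assumed), the follow-up-only half-width is 0.640 SD. ANCOVA gives 0.650, 0.620, 0.563 and 0.464 SD at the same four correlations, with break-even at about 0.17.

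**The case against.** The strongest reply is that this concerns efficiency on secondary endpoints, not validity, and that the gain is unverified. Nothing in the documents shows which correlation applies. At r = 0.3 the interval narrows by only 3.5%, and near 0 it widens by about 1%. This stands, and it limits the weight of the point.

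A second reply is that the plan is not silent on inference. It has a two-tailed rule and promises 95% intervals, and descriptive reporting of five secondary instruments is defensible in a 50-subject post-market study. That is fair. What remains open is the model and the effect measure.

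Third, preoperative collection is inferred. The synopsis endpoint row also mentions a direct postoperative visit, so a reference to every visit may not be literal for every instrument. This stands too, and the fix has to be limited to scores with a valid preoperative value.

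Fourth, the figures assume a linear relation and well-behaved residuals. The simulation used normal data, whereas these scores may be skewed, and the Descriptive analysis section itself allows for non-normal continuous data. The gains at r = 0.5 to 0.7 may therefore be optimistic.

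A reader might infer more than the documents support:

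- That an unadjusted comparison would be biased or invalid. Randomisation makes it valid.
- That a known amount of precision is being lost. Without r, only a range can be given.
- That ANCOVA needs at least a moderate correlation to help at all. That condition concerns a material gain over follow-up scores alone; against a change score the gain is largest at low r.
- That 2 years should be the main time point for the scores. The third secondary endpoint covers all visits and ranks none of them.

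**Conclusion.** The point holds in a limited form. The plan states no between-arm model and no baseline adjustment for the five scores, although it apparently collects the covariate that would serve. Whether the alternative is follow-up scores alone or change scores decides how much ANCOVA gains, and the plan specifies neither. Against follow-up scores alone, the effect on interval width runs from about 1% wider at r = 0 to 28% narrower at r = 0.7; against change scores ANCOVA is narrower throughout that range. The trade is favourable because the possible loss is small and the possible gain is not.

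The size rests on the assumed correlation, equal SDs for the change-score figures, a linear relation, and 25 per arm with full follow-up. Only secondary endpoints are touched, and the primary RSA conclusion does not change. The change is worth making but is not critical to the trial.

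**What to change.** In the Descriptive analysis and the Primary and Secondary Endpoint Analysis sections, state that:

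- each score with a valid preoperative value is compared between the randomised arms at each follow-up visit where it is collected, by ANCOVA with that preoperative value as covariate;
- the adjusted difference and its 95% CI are reported beside the planned descriptive table;
- a subject whose preoperative value is missing is kept by using the mean preoperative value over both arms;
- scores without a valid preoperative value, possibly the Forgotten Joint Score, are compared unadjusted.

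The plan should also list which instruments are taken before surgery. If one main time point is wanted, the sponsor should name it in advance.

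The cost is a short SAP paragraph, one degree of freedom per model, and an interval about 1% wider if the correlation is near 0. No new data are needed for any score already taken preoperatively.

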### **Primary and Secondary Endpoint Analysis**

Analysis for primary and secondary endpoints will use the patient population which consists of those cases with complete data for one or more of the primary and secondary endpoints.

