### **Study Safety**

All adverse events will be recorded, described, and compared for the groups. Comparisons will use standard statistical tests (chi-square, Fisher’s exact). Adverse events resulting in device removal and/or revision and those not requiring device removal and/or revision will be summarized. Device related serious adverse events will be collected and evaluated for differences in the population.

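### The primary-analysis population is set by complete data on any one endpoint, conflicts with the stated analysis labels, and leaves stems revised or lost before two years without a rule in the migration comparison

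*Combined protocol and SAP*

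**What the plan says.** The synopsis (Study Objectives/Endpoints) sets the "Primary endpoint: Migration of the prosthesis over two years based on RSA data". Under Materials and Methods, "Follow-up will take place at 6-weeks, 1 and 2 years postoperatively". Statistical Reporting says only that migration is evaluated by RSA. It names no test, model, time point or missing-data rule.

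Two statements in the statistical part define who is analysed:

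- Statistical Method: "Data will be presented as per protocol (intention-to-treat) and as treated analysis (treatment eventually received".
- Primary and Secondary Endpoint Analysis: one population for all endpoints, "those cases with complete data for one or more of the primary and secondary endpoints".

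Revised stems appear elsewhere. A secondary endpoint is "Survival of the hip prosthesis within 2 years", assessed by Kaplan-Meier (Survivorship). Study Safety adds: "Adverse events resulting in device removal and/or revision and those not requiring device removal and/or revision will be summarized".

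**The concern.** There are two linked problems.

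**The sets are not reconciled.** Intention-to-treat keeps subjects in the arm to which they were randomised. Per protocol drops those who departed from the protocol. The plan gives them as one set. It then defines a third population by data completeness and does not say how that relates to the other two, so the reader cannot tell which set carries the primary result.

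**A revised or lost stem has no stated role in the migration comparison.** A stem revised at, say, 14 months has no two-year RSA value for the original implant. The plan could exclude it, use its earlier values in a longitudinal model, carry a value forward or count it as a failure, and no section chooses. If complete two-year values are compared, it is left out. Stems revised for loosening or migration are likely to be high migrators, so leaving them out makes their arm look more stable than it was. The survival analysis and the adverse event summary would show an imbalance in revisions but would not correct the migration estimate.

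**Working it through.** **1. Does the population rule decide who enters the migration comparison?** It does not. One secondary endpoint is "The prevalence of malalignment, incorrect sizing, subsidence and intraoperative fractures at the direct postoperative visit". An operated subject can be complete on that endpoint alone and so belong to the population with no follow-up RSA value. Belonging to the population is therefore not the same as contributing to the primary comparison.

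**2. Inputs for an illustration.** From the documents: "50 subjects in total, 25 study subjects implanted with the study device per cohort", and two-sided testing at 0.05. Assumed, because the documents give none of them: normal migration values with SD 1, a t-test on complete two-year values, a true difference of 0.8 SD, and one or two losses. The plan states no power or effect size, so there is no figure of its own to reproduce. The 0.8 SD is chosen because it is close to what 25 per arm detects with 80% power: (1.960 + 0.842) × √(2/25) = 2.802 × 0.283 = 0.79 SD.

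**3. Effect of dropping stems from the higher-migration arm.** Removing the highest of 25 values lowers that arm's mean by 0.082 SD. Removing the two highest lowers it by 0.152 SD. The expected differences are 0.80 − 0.082 = 0.72 SD and 0.80 − 0.152 = 0.65 SD. The second is the upper bound on the bias from two losses in one arm. The intermediate rows let the chance of loss rise by a factor of 1.65 (moderate) or 2.7 (strong) per SD of migration. Results are from simulation with 40,000 replicates.

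| Two stems lost, higher-migration arm | Expected difference | Power | Significance verdict changed | False-positive rate if no true difference |
|---|---|---|---|---|
| No loss | 0.80 SD | 79% | – | about 5% |
| Random | 0.80 SD | 78% | 5% | 4.9% |
| Moderately related | 0.76 SD | 74% | 7% | 5.2% |
| Strongly related | 0.73 SD | 70% | 9% | 6.0% |
| The two highest (upper bound) | 0.65 SD | 64% | 15% | 9.3% |

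In the last column the two stems are lost from one arm only. With one stem lost, the differences are 0.80, 0.78, 0.76 and 0.72 SD, and power is 78%, 77%, 75% and 72%.

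**4. Direction.** If the two highest stems are lost from the lower-migration arm instead, the expected difference rises to 0.80 + 0.152 = 0.95 SD and is overstated.

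**5. How much a mixed model recovers.** Suppose the two-year value is missing, and visits have equal correlation ρ. The share of bias recovered is close to the squared multiple correlation of the two-year value with the visits observed:

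- Both earlier visits observed, 2ρ²/(1 + ρ): for ρ = 0.5, 0.5/1.5 = 33%; for ρ = 0.7, 0.98/1.7 = 58%; for ρ = 0.9, 1.62/1.9 = 85%.
- Only the 6-week visit observed, ρ²: 25%, 49% and 81%.

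Simulation agrees. With both visits it gives 31–85%. With only the 6-week value and the two highest stems lost it gives slightly less than the formula, about 21–77%. Overall, recovery is roughly 20–85%.

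**The case against.** A reader might infer that the plan excludes revised stems from its primary analysis, or that its primary result will be biased. The documents do not support either. The population rule needs completeness on only one endpoint, and the wording of the primary endpoint, with three follow-up visits, also fits a longitudinal analysis. The bias arises only if complete two-year values are compared and loss is related to migration.

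The largest figures need the two highest migrators of 25 to be lost from one arm. With two moderately related losses the estimate moves by 0.04 SD, and the false-positive rate is 5.2% against 4.9% for random loss. Those are small effects.

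The label in Statistical Method may be loose wording for as allocated versus as received. The completeness rule may mean available cases for each endpoint. Both are plausible readings, and a clarification along those lines would settle the labels. It would still leave open what happens to a stem revised before two years.

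Revisions are also visible in the survival endpoint and the safety summary. That stands as a safeguard on reporting, but not as a correction of the migration estimate.

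**Conclusion.** The concern holds as an unreconciled population definition together with a missing rule. It does not show that the result will be biased. The two population statements conflict as written, and neither they nor any other section says how a stem revised or lost before two years enters the primary comparison.

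The consequence is conditional. If complete two-year values are compared, two losses from the higher-migration arm lower the expected difference from 0.80 SD by nothing (random loss), by 0.04 SD (moderately related) or by at most 0.15 SD. Power falls from 79% to 78%, 74% or 64%. Losses in the other arm reverse the bias. These figures rest on assumed normality, effect size, test and number of losses. With no revision or loss rate in the documents, the actual size and direction are unknown.

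The point should be fixed, because the choice is cheap now and is most credible when made before outcomes by arm are known. The case rests on the missing rule, not on the worst-case figures.

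**What to change.** For the primary endpoint, replace both the completeness rule and the combined per-protocol/intention-to-treat label with the following:

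- **Population:** all randomised subjects with any postoperative RSA migration value, analysed as randomised. The as-treated analysis is supportive.
- **Analysis:** compare the arms at two years on one migration variable named in advance. Use a repeated-measures mixed model (treatment, visit, treatment-by-visit) with all RSA values up to revision or loss.
- **Reporting:** tabulate by arm the randomised subjects with no RSA migration value, and the number of missing two-year values with the reason for each.
- **Optional sensitivity analysis:** a two-year rank test that places stems revised for loosening or migration worst, with the reason classified without knowledge of arm where possible. State that leaving out other losses assumes they are unrelated to two-year migration within arm, which is a stronger assumption than missing at random given earlier RSA values.

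**Cost:** SAP wording and one model, plus one test if the option is taken. No new data are needed if RSA is taken at the planned follow-up visits; the documents do not state the RSA schedule.

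**Limits:** The population still depends on having at least one RSA value, hence the tabulation. The mixed model assumes missing at random and recovers only part of any bias, roughly 20–85% in the illustration, depending on the correlation between visits and how many precede the loss. The rank test gives no estimate in millimetres and is sensitive to misclassified reasons: if two unrelated revisions in one arm are ranked worst, its false-positive rate is about 6%.
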